Title	An Active Surveillance, Post-Authorization Safety Study (PASS) to Estimate Incidence Rates of Serious Infection, Malignancy, Cardiovascular (CV) and Other Safety Events of Interest among all Patients Treated with Ruxience for Rheumatoid Arthritis (RA) within the British Society for Rheumatology Biologics Register-Rheumatoid Arthritis (BSRBR-RA).
Protocol number	B3281011
Protocol version identifier	v.1
Date	14 October 2020
EU Post Authorisation Study (PAS) Register Number	TBD
Active substance	PF-05280586 Rituximab
Medicinal product	Ruxience (rituximab)
Product reference	H0004696
Procedure number	EMA/H/C/004696/0000
Marketing Authorisation Holder (MAH)	Pfizer Europe MA EEIG
Joint PASS	No
Research question and objectives	Research Question: What are the incidence rates of safety events of special interest in patients with rheumatoid arthritis who are enrolled in the in the BSRBR-RA and initiate treatment with Ruxience?

090177e1953dcb50\Approved\Approved On: 16-Oct-2020 13:28 (GMT)

PFIZER CONFIDENTIAL

	Objectives: To estimate incidence rates of infections, including serious infections, malignancies, cardiovascular events, and events associated with use during pregnancy among patients with rheumatoid arthritis in the BSRBR-RA who initiate Ruxience.
Country(ies) of study	United Kingdom
Author	[name], PhD, MPH Safety Surveillance Research, Worldwide Medical and Safety, Pfizer, Inc. [name]

Marketing Authorisation Holder(s)	Pfizer Europe MA EEIG [name]
MAH contact person	[name], PhD, MPH [name]

This document contains confidential information belonging to Pfizer. Except as otherwise agreed to in writing, by accepting or reviewing this document, you agree to hold this information in confidence and not copy or disclose it to others (except where required by applicable law) or use it for unauthorized purposes. In the event of any actual or suspected breach of this obligation, Pfizer must be promptly notified.

090177e1953dcb50\Approved\Approved On: 16-Oct-2020 13:28 (GMT)

2. LIST OF ABBREVIATIONS

Abbreviation	Definition
ACR	American College of Rheumatology
ACS	Acute coronary syndrome
ADA	Adalimumab
AE	adverse Event
BSRBR	British Society for Rheumatology Biologics Register
BSRBR-RA	British Society for Rheumatology Biologics Register Rheumatoid Arthritis
CI	confidence interval
CLL	Chronic lymphocytic leukaemia
csDMARD	Conventional Synthetic Disease Modifying Anti-rheumatic Drug
CV	cardiovascular
CVD	cardiovascular disease
DALYS	Daily-adjusted Life Years
DAS-28	Disease Activity Score 28
DMARD	disease modifying anti-rheumatic drug
EEIG	European Economic Interest Grouping
EMA	European Medicines Agency
ENCePP	European Network of Centres for Pharmacoepidemiology and Pharmacovigilance
ETA	etanercept
EU	European Union
GPA	Granulomatosis polyangiitis
HRQoL	Health-related Quality of Life
ICD	International Classification of Diseases
IEC	Independent Ethics Committee
INF	infliximab
IRB	Institutional Review Board
MA	Market Authorisation
MACE	Major acute cardiovascular events
MAH	Market Authorisation Holder
MedDRA	Medical Dictionary for Regulatory Activities
MPA	Microscopic polyangiitis
NHL	Non-Hodgkin's lymphoma
NI	Non-Interventional

PFIZER CONFIDENTIAL

CT24-WI-GL02-RF02 2.0 *Non-Interventional Study Protocol Template For Secondary Data Collection Study*

01-Jun-2020

Page 5 of 34

090177e1953dcb50\Approved\Approved On: 16-Oct-2020 13:28 (GMT)

Abbreviation	Definition
NICE	National Institute for Health and Clinical Excellence
NMSC	non-melanoma skin cancer
NSAIDs	non-steroidal anti-inflammatory drugs
PAS	Post-Authorisation Study
PASS	Post-Authorization Safety Study
PV	Pemphigus Vulgaris
RA	Rheumatoid Arthritis
QALY	Quality-adjusted Life Year
RMP	Risk management plan
SAP	Statistical Analysis Plan
SMQ	Standardised MedDRA Queries
TNF	tumor necrosis factor
TNFi	tumor necrosis factor inhibitor
UK	United Kingdom

4. ABSTRACT

Title: An Active Surveillance, Post-Authorisation Safety Study (PASS) to Estimate Incidence Rates of Safety Events of Special Interest among all Patients Treated with Ruxience for Rheumatoid Arthritis (RA) within the British Society for Rheumatology Biologics Register-Rheumatoid Arthritis (BSRBR-RA).

Version: 1

Date: 14 October 2020

Main Author: [name], PhD, MPH, Pfizer, Inc.

Rationale and Background:

Rituximab is a genetically engineered chimeric mouse/human monoclonal IgG1k antibody targeting the transmembrane CD20 antigen. CD20 is a 32-kDa, non-glycosylated transmembrane phosphoprotein, located on the surface of normal precursor-B cells, mature B lymphocytes and malignant B cells. The natural ligand for CD20 has not been identified, and the biological function of CD20 remains unclear. Rituximab binds to a discontinuous conformational epitope on CD20 and initiates multiple immune effector functions leading to target cell lysis. The currently approved indications for licensed rituximab (MabThera) are for Rheumatoid arthritis (RA), Non-Hodgkin's lymphoma (NHL), Chronic lymphocytic leukaemia (CLL), Granulomatosis with polyangiitis (GPA), Microscopic polyangiitis (MPA) and Pemphigus Vulgaris (PV).¹

Licensed as MabThera in the European Union (EU) in 1998, rituximab was the first biologic on the market for RA for specific B cell targeting therapy. Rituximab in combination with methotrexate is indicated for the treatment of adult patients with severe active RA who have had an inadequate response or intolerance to other disease modifying anti-rheumatic drugs (DMARDs) including one or more tumour necrosis factor (TNF) inhibitor therapies. Approved in the EU on 1 April 2020, PF-05280586 (Ruxience) has been developed by Pfizer as a biosimilar to the licensed reference product, MabThera. Pfizer proposes the assessment of safety events of special interest based on the Ruxience Risk Management Plan (RMP) v. 1.0 (infections including serious infections (Important Identified Risk), malignancies (Important Potential Risk), impact on cardiovascular disease (CVD) (Important Potential Risk) and use in pregnancy (Missing Information)).² This protocol describes a post-authorisation safety study (PASS) of Ruxience-exposed patients using actively collected prospective data included in the established BSRBR-RA. This study is designated as a Category 4 "Additional Pharmacovigilance Activities" in line with the reference product.

Research Question: What are the incidence rates of safety events of special interest in patients with rheumatoid arthritis who are enrolled in the in the BSRBR-RA and initiate treatment with Ruxience?

Objectives: To estimate incidence rates of infections, including serious infections, malignancies, cardiovascular events, and events associated with use during pregnancy among patients with rheumatoid arthritis in the BSRBR-RA who initiate Ruxience.

Study Design: This is an active surveillance study using existing data within the BSRBR-RA, an ongoing, prospective, observational cohort study started in 2001 with the primary aim of studying the safety of new therapies for RA during routine post-marketed clinical use.

Population: The study population will comprise all patients with RA enrolled within the BSRBR-RA who initiate treatment with Ruxience.

Data Sources: The BSRBR-RA was established in 2001 to study the safety of biologic therapies in RA patients living in the United Kingdom (UK).

Variables: This study will focus on specific variables routinely captured in the BSRBR-RA and include baseline patient characteristics (ie, clinical and demographic characteristics, comorbidities and current and past therapies), and safety events of special interest including serious infections, malignancies, CV events, and events associated with use during pregnancy.

Study Size: This is a descriptive study without pre-specified hypotheses, therefore there is no minimum sample size requirement. All Ruxience-treated patients with data in the BSRBR-RA during the study period will be included in this study.

Study Period: The Study Start Date is defined as the date when the first patient entered in the BSRBR-RA with RA initiates Ruxience. The Study End Date is defined as 3 years after the Study Start Date.

Data Analysis: Annual reports will consist of descriptive summaries of uptake of patients exposed to Ruxience and baseline variables. The final report will consist of incidence rates of safety events of interest described above for Ruxience-treated patients. No comparative analyses with other cohorts will be performed.

Milestones: The first annual report describing the number and characteristics of patients initiating Ruxience is estimated by 31 July 2021 and annually thereafter through 31 July 2023. A final report estimating incidence rates of events of special interest is expected by 31 December 2023.

5. AMENDMENTS AND UPDATES

None.

090177e1953dcb50\Approved\Approved On: 16-Oct-2020 13:28 (GMT)

6. MILESTONES

Deliverable	Estimated Timeline
Registration in the EU PAS Register	TBD
Start of data collection (estimated)	31-May-2021 [^]
Date of first annual report (estimated)	31-July-2021
Date of second annual report (estimated)	31-July-2022
Date of third annual report (estimated)	31-July-2023
End of data collection (estimated)	31-July-2023 [#]
Final report (estimated)	31 December 2023 ^x

[^] Start of data collection is the planned date for starting data extraction for the purposes of the first annual report.

[#] End of data collection is the planned date on which the analytical dataset will be first completely available; the analytic dataset is the minimum set of data required to perform the statistical analysis for the primary objective(s).

^x Final report must be prepared within 11 months of end of data collection.

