9.4. Data Sources

BSRBR is the source of core baseline data, including patient demographics and disease characteristics collected by the recruiting clinician, using a standardised form.

Follow up

BSRBR data are the source of information on anti-rheumatic treatment, updated every 6-12 months depending on how long a patient has been in the register (6 monthly for the first 3 years and 12 monthly thereafter). This change is to reduce the burden of data capture on study sites, but the same data are collected at each follow-up. As many patients starting Ruxience will have been enrolled previously when they started Mabthera, follow-up may only be every 12 months. Some patients starting Ruxience as their first anti-B cell therapy will provide data more often as per the BSRBR protocol and some trusts may decide themselves to reconsent patients each time they switch drugs and send data every 6 months for 3 years again. Data captured includes continuation on drug and dates and reasons for stopping, with details of any change in dose and commencement of any new co therapy. Clinical information to permit calculation of the Disease Activity Score in 28 joints (DAS-28) is also collected.

Endpoints

BSRBR data include reports of serious morbidity reported directly by the rheumatology team at each scheduled follow-up date. For serious events additional data are captured, either against a pre-specified set of questions for certain events of special interest or using an open request for additional data. All events included in this protocol are considered events of special interest. All serious morbidities reported to BSRBR are coded by a trained nurse using the Medical Dictionary for Regulatory Activities (MedDRA).

BSRBR is linked to the UK national death and cancer registers which allow the “flagging” of individuals such that if they die or are entered in a cancer register, the BSRBR-RA learns of the event and obtains death certificate details or cancer register details. These data are held in a separate secure data safe haven at the University of Manchester. On average deaths are usually reported within 1 week to the national register although cancers can take much longer due to the structure of national reporting. BSRBR-RA received a download of death and cancer on average once/year.

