9.7. Data Analysis

All statistical analyses will be performed by BSRBR using Stata. The annual analyses will include all patients who have received Ruxience (baseline characteristics) and event incidence reports will include all patients with study follow-up data.

Analyses will be undertaken at 12 monthly intervals and will include recruitment details, baseline characteristics and crude event rates.

The final analysis will provide the incidence rates of safety events of interest overall. If sample size allows, additional analysis in subgroups by gender and new users versus switcher from originator will be undertaken.

The general analytic approach will be descriptive and include rates of events of interest among Ruxience-treated patients. Data will be presented as number of events, incidence rates and 95 % confidence intervals. Such analyses will be performed by and at the direction of BSRBR based on an a priori statistical analysis plan (SAP) maintained by University of Manchester and shared with the Sponsor. The codes will be harmonised with other registers conducting similar analysis. A draft set of MedDRA codes is included in:

Index Date

The Index Date is the date of Ruxience initiation. Patients who switch from another therapy to Ruxience while they are enrolled in BSRBR-RA are eligible for enrollment, and the index date will be the date of Ruxience initiation.

Risk Window

Patients will be evaluated for safety events of interest while exposed to Ruxience and accrue person-time from Index Date until the first occurrence of the event of interest, death, date of last scheduled clinical data provision to the register, lost to follow up, exit from the register or completion of 3 years of follow up. The final report will censor all patients at 3 years after Date of Study Start. Follow up will be uniquely determined for each safety endpoint of interest.

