12. PLANS FOR DISSEMINATING AND COMMUNICATING STUDY RESULTS

In the event of any prohibition or restriction imposed (eg, clinical hold) by an applicable competent authority in any area of the world, or if the investigator party responsible for collecting data from the participant is aware of any new information which might influence the evaluation of the benefits and risks of a Pfizer product, Pfizer should be informed immediately.

Annual reports will be prepared by BSRBR and shared with Pfizer. Analysis using linked register data through 3 years of follow up will be the basis for the study final report. Data may be used in regulatory communications external to the UK or for contextualisation purposes. Manuscripts based on specific endpoints of interest may be developed for publication purposes.

In the event of any prohibition or restriction imposed (eg, clinical hold) by an applicable Competent Authority in any area of the world, or if the investigator is aware of any new information which might influence the evaluation of the benefits and risks of a Pfizer product, Pfizer should be informed immediately.

In addition, the investigator will inform Pfizer immediately of any urgent safety measures taken by the investigator to protect the study patients against any immediate hazard, and of any serious breaches of this NI study protocol of which the investigator becomes aware.

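### The 31 July 2023 dataset date does not secure the three-year linked data: it fits only a first Ruxience start by 31 July 2020 and leaves at most 121 days for forms and cancer linkage

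*Protocol*

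**What the plan says.** The Abstract (Section 4, Study Period) ties both ends of the study to an event: "The Study Start Date is defined as the date when the first patient entered in the BSRBR-RA with RA initiates Ruxience", and "The Study End Date is defined as 3 years after the Study Start Date". It gives no calendar date for that first initiation. Section 9.7 (Risk Window) applies the same limit to the analysis: "The final report will censor all patients at 3 years after Date of Study Start". Section 12 adds: "Analysis using linked register data through 3 years of follow up will be the basis for the study final report".

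Section 6 works in calendar dates instead. The row reads "End of data collection (estimated) 31-July-2023", and its footnote says that "End of data collection is the planned date on which the analytical dataset will be first completely available". The final report is planned for 31 December 2023, with an outer limit of 11 months after the end of data collection.

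Section 9.4 describes how data arrive. Forms come six-monthly for a patient's first three years in the register and yearly after that. For the many patients already enrolled on MabThera, "follow-up may only be every 12 months". Death and cancer downloads arrive about once a year. Cancer registration can lag well behind death registration, by an amount that is not given.

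Section 9.7 also says when person-time stops. The general rule includes the last scheduled supply of clinical data, and the 270-day window for serious infections and cardiovascular events has a similar stop. The paragraph on NMSC and other malignancies names only the first event, loss to follow-up and completion of three years.

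**The concern.** A floating study period is paired with a calendar date for the complete dataset, and nothing in the protocol links them. If the first initiation came too late, the dataset would be declared complete before the study period had ended. If it came early enough, the time between Study End and the dataset date could still be shorter than one reporting cycle.

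The consequence differs by endpoint. Where person-time stops at the last data supply, missing forms shorten follow-up but remove events and time together. Where person-time runs on without the events having been linked, the denominator is complete and the numerator is not, so the rate is too low. That second case is malignancy, an important potential risk in the risk management plan and an endpoint for which Section 9.9 already concedes that three years may be too short.

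**Working it through.** **Inputs.** Dataset date: 31 July 2023 (Section 6). Study End: Study Start plus 3 years (Section 4). Earliest conceivable start: 1 April 2020, from "Approved in the EU on 1 April 2020, PF-05280586 (Ruxience) has been developed by Pfizer". Protocol date: 14 October 2020. Planned report: 31 December 2023 (Section 6). Form interval: 6 or 12 months; download interval: about 12 months (Section 9.4).

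**Reproducing the plan's date.** This cannot be done, because no Study Start date is given. Solving backwards, 31 July 2023 minus 3 years is 31 July 2020, the latest start that fits.

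**Slack = 31 July 2023 − (Study Start + 3 years).**

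| Assumed first start | Study End | Slack |
|---|---|---|
| 1 April 2020 (approval) | 1 April 2023 | +121 days |
| 31 July 2020 (break-even) | 31 July 2023 | 0 days |
| 14 October 2020 (protocol date) | 14 October 2023 | −75 days |
| 1 January 2021 (illustrative) | 1 January 2024 | about −5 months, one day after the planned final report |

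**Form coverage at Study End.** Assumption, not in the protocol: form dates are spread evenly over the interval I. With slack L, the share of patients with a form covering Study End is L/I, and the mean uncovered time is (I − L)²/(2I).

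- Best case, 12-monthly forms: 121/365.25 = 33% covered. Taking L as 4 months, the mean gap is (12 − 4)²/24 = 2.7 months and the largest is 8 months.
- Best case, 6-monthly forms: 121/182.6 = 66% covered. The mean gap is (6 − 4)²/12 = 0.3 months and the largest is 2 months.
- Break-even start: essentially none covered. The mean gaps are 6 months (12-monthly) and 3 months (6-monthly).

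**Linkage.** A yearly download at an arbitrary date has a chance of about 121/365.25, or one in three, of falling in the best-case window. Registration delay comes on top.

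**Effect on the malignancy rate.** With a constant rate, if a fraction f of person-time lies after the last complete linkage and a fraction m of the cancers arising there are missed, the estimated rate is the true rate × (1 − f·m). As an illustration, take the best-case start and the earliest timing of the last download, 12 months before the dataset date. Then 12 − 4 = 8 months before Study End are unlinked. For a patient who started on the first day, f = 8/36 = 22%. If linkage were the only source (m = 1), that patient's contribution would be 22% too low. Later starters have a larger f. The protocol gives no value for m.

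**The case against.** The strongest reply is that no printed sum is wrong. Study Start is unknown, and a first initiation between 1 April and 31 July 2020 would let the calendar period end by the dataset date. The milestones are labelled as estimates and could move with an event-driven Study End. This stands, so the conclusion must be conditional. It does not remove the defect, because the protocol contains no rule that moves the dataset date. The 11-month allowance, to about 30 June 2024, extends report writing and not dataset completion.

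A reader might infer that three years of follow-up will certainly not be delivered. The documents do not support that without a start date. Nor do they support treating 31 May 2021 as a study start: Section 6 defines it as the start of data extraction for the first annual report.

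A reader might also infer that all event rates will be biased. For infections and cardiovascular events, the stop at last data supply takes uncovered time out of the denominator, so the cost is mainly precision. Some patients will also report six-monthly, where the shortfall is smaller.

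For malignancy, it can be argued that the general stopping rule still applies and that clinics and patients also report cancers (Section 9.8). Both points reduce the bias. Neither removes it, since the last form date is not the last linkage date.

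Finally, three years is openly a study period. A reader might infer that every patient was promised three years, but Section 9.7 states the common cut plainly.

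**Conclusion.** The point holds in conditional form. The dataset date covers the three-year study period only with a first start on or before 31 July 2020, which the protocol does not state. Slack is 121 days at the very most and is negative by 75 days for a start on the protocol date. Against yearly forms and yearly downloads, the timetable does not secure the data that Section 12 makes the basis of the final report.

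The date arithmetic needs no assumption beyond the start date. The coverage shares assume evenly spread forms. For malignancy the direction of the error is downward, but its size cannot be fixed from the documents because entry pattern, registration delay and reporting outside linkage are not given.

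This should be fixed, but it does not invalidate the study, which is descriptive, voluntary and without a comparator.

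**What to change.** State the Study Start date, or the best estimate of it. Then take one of two routes:

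1. Define end of data collection as Study End plus at least one form cycle and one death and cancer download. About 12 months is a working assumption; because the cancer delay is not quantified, the register should confirm it.
2. Keep 31 July 2023 and set the analysis cut at the last date covered by received forms and completed linkage.

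In either case, stop person-time for NMSC and other malignancies at the last complete linkage date, and say so in the malignancy paragraph of Section 9.7. Describe follow-up as *up to 3 years*, since the common cut allows only first-day starters to reach three years, and report the observed median.

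The cost is a later final report under the first route or a shorter stated follow-up under the second, plus text edits. No new data collection is needed.

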7. RATIONALE AND BACKGROUND

RA is a chronic and systemic inflammatory disease with an estimated prevalence of 0.5-1.0% and a mean annual incidence of 0.02-0.05% within Northern European and North American populations.³ RA is characterised by inflammation, joint destruction, and progressive disability. Joint destruction is frequently irreversible resulting in significant cumulative morbidity. Patients experience a broad range of co-morbidities.⁴ Compared with the general population, RA patients are at a higher risk of infections, CV disease (CVD) and malignancies (including lymphoma).^{5,6,7,8,9,10,11,12,13} These patients are also treated with multiple classes of agents, including non-steroidal anti-inflammatory drugs (NSAIDs), glucocorticoids, and DMARDs including biologicals, each of which carry significant risks as well as benefits.

Rituximab is a genetically engineered chimeric mouse/human monoclonal IgG1k antibody targeting the transmembrane CD20 antigen. CD20 is a 32-kDa, non-glycosylated transmembrane phosphoprotein, located on the surface of normal precursor-B cells, mature B lymphocytes and malignant B cells. The natural ligand for CD20 has not been identified, and the biological function of CD20 remains unclear. Rituximab binds to a discontinuous conformational epitope on CD20 and initiates multiple immune effector functions leading to target cell lysis. The currently approved indications for licensed rituximab (MabThera) are for Rheumatoid arthritis (RA), Non-Hodgkin's lymphoma (NHL), Chronic lymphocytic leukaemia (CLL), Granulomatosis with polyangiitis (GPA), Microscopic polyangiitis (MPA) and Pemphigus Vulgaris (PV).²

Licensed as MabThera in the European Union (EU) in 1998, rituximab was the first biologic on the market for RA for specific B cell targeting therapy.¹⁴ Rituximab in combination with methotrexate is indicated for the treatment of adult patients with severe active RA who have had an inadequate response or intolerance to other disease modifying anti-rheumatic drugs (DMARDs) including one or more tumour necrosis factor (TNF) inhibitor therapies.

Biosimilars and non-originator biologicals of rituximab have been approved in several additional countries as of July 2018, including Turkey, Russia, Argentina, South Korea, Australia, and India.¹⁵ The EMA approved two rituximab biosimilars from 2 MAHs including Rixathon (Sandoz) in June 2017, and Truxima (Celltrion) in November 2018. PF-05280586 (Ruxience) has been developed by Pfizer as a proposed biosimilar to the licensed reference product MabThera and was approved on 1 April 2020.

The Market Authorisation Holder (MAH) proposes the assessment of safety events of special interest based on the Ruxience RMP v. 1.0 (infections including serious infections (Important Identified Risk), malignancies (Important Potential Risk), impact on cardiovascular disease (CVD) (Important Potential Risk) and use in pregnancy (Missing Information)).²

This study is designed as a Post-authorisation Safety Study (PASS) and is conducted voluntarily by Pfizer. This study is designated as "Category 4 Additional Pharmacovigilance Activities" in line with the reference product.

